8.2 Assay timepoints

Endpoint assays for immunologic and virologic responses will be performed on a subset of participants to be determined by the outcome of primary objectives and endpoints.

8.3 Endpoint assays: cellular

8.3.1 Intracellular cytokine staining (ICS) assay

Flow cytometry will be used to examine HIV-specific CD4+ and CD8+ T-cell responses following stimulation of PBMCs with synthetic HIV peptides that span the HIV-1 viral proteins. ICS parameters will include cytokines such as interferon gamma (IFN- γ), interleukin (IL)-2, and TNF- α , and may include other cytokines (such as cytokines relevant to Th2 and Th17 responses) to identify T cells of specific functionality. Data will be reported as percentages of CD4+ and CD8+ T cells responding to a specific peptide pool. Additional cell surface markers, cytokines, or functional markers may also be analyzed.

8.4 Phenotyping of cell populations

Phenotyping of dendritic cells, monocytes, NK cells, B cells, T cells, or other leukocytes for lineage, maturation, and activation markers by flow cytometry may be performed on PBMCs. Data will be reported as percent of cells positive for each marker at the various timepoints.

8.5 Endpoint assays: humoral

8.5.1 Neutralizing antibody assay

HIV-1–specific nAb assays will be performed on serum samples from study participants. The TZM-bl assay will test neutralization of the autologous transmitted/founder virus and a panel of heterologous tier 2 viruses (118, 119). Autologous neutralization escape may also be assessed at the discretion of the HVTN Laboratory Center, contingent on the results of the nAb assays.

8.5.2 Antibody-dependent cellular cytotoxicity (ADCC)

ADCC activity may be assessed using serum samples from study participants. For the Luciferase-based cytotoxicity assay, participant sera are incubated with infectious molecular clone (IMC)-infected cells and percent killing is measured by evaluating the reduction in the luminescence signal after incubation of infected-target and effector cells in presence of serum Ab.

8.5.3 Antibody-dependent cellular phagocytosis (ADCP)

To assess the ability of antibodies to engage cellular FcR for potential antiviral function, ADCP may be measured using serum samples from study participants. ADCP is measured by assessing the ability of antibodies to mediate monocyte phagocytosis of HIV-1 antigen coated fluorescent beads by flow cytometry (120, 121). An array of antigens or viruses may also be analyzed at the discretion of the HVTN Laboratory Center, which may be contingent on the results of the primary antigens or viruses.

8.5.4 Virion capture

The ability of purified IgG from participant serum to mediate infectious virion capture will be measured by infectious virion capture assay (IVCA). The test uses a Protein G column-based capture of Ig-virion immune complexes.

8.6 HIV viral reservoir

Changes in the HIV reservoir will be quantitated in CD4+ T cells purified from PBMCs at designated timepoints, using testing methods such as the Intact Proviral

DNA Assay (IPDA), *Tat/rev* Induced Limiting Dilution Assay (TILDA), assays detecting replication-competent virus-bearing cells (eg, virus outgrowth assays), and/or measures of total proviral DNA. Cell-associated HIV-RNA may be quantitated as a measure of the transcriptionally active reservoir.

8.7 Host genomics

HLA and CCR5 genotyping may be performed on samples from this study or HVTN 703/HPTN 081 using cryopreserved PBMC. Other genes, including those associated with immune responses (eg, immunoglobulin or T-cell receptor genes) or HIV-1 disease progression may also be assessed.

8.8 HIV antiretroviral resistance testing

HIV antiretroviral resistance testing will be performed by RNA sequencing for resistance mutations in participants whose plasma viremia shows limited suppression after ART re-initiation.

8.9 ARV detection

Blood specimens will be collected during treatment interruption for ARV detection and drug level testing. ARV drug levels may be assessed at the discretion of the protocol team for participants who have not met virologic and non-virologic criteria for transition from monitoring ATI (Schedule 1) to monitoring ATI with viremia (Schedule 2) or for ART re-initiation (from Schedule 2 to Schedule 3). Assay methods may include HPLC-mass spectrometry, reverse-phase HPLC coupled with tandem mass spectrometry, or another similar method.

8.10 Biohazard containment

As the transmission of HIV and other blood-borne pathogens can occur through contact with contaminated needles, blood, and blood products, appropriate precautions will be employed by all personnel in the drawing of blood and shipping and handling of all specimens for this study, as currently recommended by the CDC and the NIH or other applicable agencies.

All dangerous goods materials, including Biological Substances, Category A or Category B, must be transported according to instructions detailed in the International Air Transport Association Dangerous Goods Regulations.

9 Research use of stored human samples and/or data

9.1 Specimen storage and other use of specimens

The HVTN and HPTN store specimens from all study participants indefinitely, unless a participant requests that specimens be destroyed or if required by IRB/EC, or RA.

Other use of specimens is defined as studies not covered by the protocol or the informed consent form for the main study (see [Appendix A](#) and [Appendix C](#)).

This research may relate to HIV, vaccines, antibodies, the immune system, and other diseases. This could include genetic testing and, potentially, genome-wide studies. This research is done only to the extent authorized in each study site's informed consent form, or as otherwise authorized under applicable law. Other research on specimens ("other use") will occur only after review and approval by the Networks, the IRB/EC of the researcher requesting the specimens, and the IRBs/ECs/REs of the CRSs if required.

As part of consenting for the study, participants document their initial decision to allow or not allow their specimens to be used in other research, and they may change their decision at any time. The participant's initial decision about other use of their specimens, and any later change to that decision, is recorded by their CRS in a Web-based tool that documents their current decisions for other use of their specimens. The Networks will only allow other research to be done on specimens from participants who allow such use.

CRSs must notify HVTN Regulatory Affairs if institutional or local governmental requirements pose a conflict with or impose restrictions on specimen storage or other use of specimens.

9.2 Exploratory studies

Samples may be used for other testing and research related to furthering the understanding of HIV, immunology, antibodies, or vaccines. In addition, cryopreserved samples may be used to perform additional assays to support standardization and validation of existing or newly developed methods.

10 Potential risks and benefits

10.1 Potential risks

10.1.1 Risks of ATI

The risks from a closely monitored ATI are minimal in this study population. There is a theoretical risk that such an interruption could lead to the development of HIV drug resistance (122). This may be a particular concern for individuals taking NNRTIs. However, this potential risk is substantially mitigated by the procedures described in Section 6.1.1. Given the study population as restricted by the eligibility criteria, the frequency of immunological and virologic monitoring, and the criteria for restarting ART, it is extremely unlikely that such an ART interruption will lead to the development of any opportunistic infections or AIDS-defining conditions.

Rarely, viremic rebound may be associated with ARS (see Section 6.7.2).

During the ATI phase, participants may transmit HIV infection if they do not adhere to safer sex practices.

10.1.2 Phlebotomy

Drawing blood may be associated with discomfort, bruising, local hematoma formation and, on rare occasions, infections, lightheadedness, and fainting.

The amount of blood drawn for research purposes will be within regulatory limits (see 21 CFR 630.15).

10.2 Potential benefits

Study participants should expect no direct health benefits from study participation. Knowledge gained in this study may aid in development of better interventions against HIV.

11 Monitoring of safety

11.1 Safety monitoring and oversight

11.1.1 HVTN 805/HPTN 093 PSRT

The HVTN 805/HPTN 093 PSRT is composed of the following members:

- DAIDS medical officer representatives
- Protocol chairs
- Protocol Team leaders
- Core medical monitor
- Clinical safety specialist
- Regional medical liaison

The Protocol Team clinic coordinator, clinical data manager, clinical trial manager, clinical research manager, and others may also be included in HVTN 805/HPTN 093 PSRT meetings.

The clinician members of HVTN 805/HPTN 093 PSRT are responsible for decisions related to participant safety.

The PSRT will review laboratory parameters (HIV-RNA, CD4+ T-cell count), adverse events, and a summary of the distribution of time to meeting ART re-initiation criteria twice a month. Once the final participant achieves viral resuppression in Schedule 3, the PSRT may consider holding less frequent reviews (ie, monthly).

The PSRT will also review the distribution of time to meeting ART re-initiation criteria in the first 20 HVTN 805/HPTN 093 participants and assess whether the distribution is comparable to that observed in an NIH intramural therapeutic HIV vaccine study that enrolled HIV-infected participants who initiated ART early with similar ART re-initiation criteria to those proposed here. Based on the NIH intramural therapeutic HIV vaccine study results, we expect that the median time to meeting ART re-initiation criteria in HVTN 805/HPTN 093 will be at ATI week 15 and that the 75th percentile for time to meeting ART re-initiation criteria will be around week 12-18. If the spread in the distribution time to meeting ART re-initiation criteria is less than expected, then the HVTN 805/HPTN 093 PSRT, in consultation with the NIAID Data and Safety Monitoring Board (DSMB), will consider strategies for modifying the study (eg, to alter the eligibility criteria) with the aim to further enrich for potential controllers.

The HVTN 805/HPTN 093 PSRT will also monitor specifically for failure to re-suppress or to demonstrate a 2-log viral load reduction within 12 weeks after ART re-initiation. Any such failure and/or any AE \geq Grade 4 deemed related to the study procedures will be reviewed by the HVTN 805/HPTN 093 PSRT promptly and, if indicated, by the NIAID DSMB to evaluate whether and how the study should be modified.

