4.1.1 Power to evaluate time to ART re-initiation criteria

Using data from the placebo arm of a therapeutic vaccine study which enrolled early treated patients (21), we modeled the time T (in weeks) to meet re-initiation criteria as a Weibull distribution with survival function $P(T > t) = \exp[-(\lambda t)^p]$, where $\lambda = \exp(-2.932) = 0.053$ and $p = 2.014$. From these parameters, we estimated the median time to meet re-initiation criteria as 15.6 weeks in the AMP placebo recipients. We can express the treatment effect in terms of either the HR θ or the factor β by which treatment increases the median time to meet re-initiation criteria; β and θ are related by $\beta = \theta^{1/p}$.

We model censoring of time to restart criteria using an exponential model and a maximum follow-up time of 72 weeks, where follow-up is censored at a rate of 20% per year due to either study termination or re-initiation of ART before reaching the restart criteria. Power for a 40%, 50%, 60%, and 70% reduction in hazard under different prevention efficacy scenarios are shown in [Table 4-1](#). These hazard reductions correspond to 29%, 41%, 58%, and 82% increases in the median time to meet restart criteria. Therefore, if VRC01 increases the median time to restart criteria 58% and the enrollment rate is 50%, then under the parent

study null hypothesis power to detect a difference in time to restart criteria is 72% while under the alternative hypothesis power is 62%.

Table 4-1 Power under different prevention efficacy results, different enrollment rates and different treatment effects, expressed as either reduction in hazard or percent increase in median time to meet re-initiation criteria

Enrollment Rate		Null hypothesis			Alternative hypothesis			
		25%	50%	75%	25%	50%	75%	
Expected number of placebos		7	13	20	9	18	26	
Expected number of VRC01		14	27	41	7	14	21	
Reduction in hazard	% Increase in median time to meet re-initiation criteria							
	40%	29%	20%	31%	44%	16%	27%	36%
	50%	41%	31%	49%	67%	23%	42%	57%
	60%	58%	46%	72%	89%	35%	62%	81%
	70%	82%	65%	90%	98%	52%	85%	95%

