8 SAMPLE SIZE

We calculate the expected trial sized under different scenarios for the percentage of enrolled participants out of the total number of endpoint infected cases from HVTN 704/HPTN 085; scenarios include 25%, 50%, and 75%. Eligible placebo recipients will be capped such that the overall placebo to VRC01 recipient ratio of enrolled participants is at most approximately 1:1. Given that the parent HVTN 704/HPTN 085 study was randomized at a 1:2 placebo to VRC01 ratio, we would only expect to cap the number of eligible placebo recipients if prevention efficacy (PE) exceeds 50%. Given this constraint, along with an assumption of a common prevention efficacy at each dose (PE10 and PE30), the expected trial size will depend on different levels of PE. Under the null hypothesis (PE10 = PE30 = 0%), the total expected number of endpoint infections among placebo recipients is 26 and VRC01 recipients is 55 (Table 4-3 in the parent protocol HVTN 704/HPTN 085); therefore, we assume a trial size of 7, 13 or 20 placebo recipients and 14, 28, or 41 VRC01 recipients depending on the enrollment ratio. Under the alternative hypothesis (PE10 = PE30 = 60%), the total expected number of endpoint infections among placebo recipients is 37 and VRC01 recipients is 30 (Table 4-3 in the parent protocol); therefore, under the different enrollment ratio scenarios, we assume a trial size of 8, 15, or 23 placebo recipients and an equal number of VRC01 recipients so as not to exceed a 1:1 ratio. These six sample size scenarios represent estimated upper and lower bounds for sample size given the expected number of endpoint infections under the null and alternative hypotheses respectively, as well as various scenarios for the percentage of eligible participants who will ultimately enroll in HVTN 804/HPTN 095.

Sample size considerations for time to ART re-initiation criteria (primary objective 1)

Using data from the placebo arm of a therapeutic vaccine study which enrolled early treated patients (80), we modeled the time T (in weeks) to meet re-initiation criteria as a Weibull

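### Protocol 11.1.1 expects a median at week 15 and a 75th percentile around week 12-18; the part of that range below week 15 is impossible, so the expectation for the first-20 review needs correcting

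*Protocol*

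**What the plan says.** Protocol 11.1.1 gives the PSRT a specific task beyond its twice-monthly reviews. Once times to the re-initiation criteria are available for the first 20 people enrolled, it is to look at how they are distributed. The stated purpose is to "assess whether the distribution is comparable to that observed in an NIH intramural therapeutic HIV vaccine study", described as one that enrolled people who started ART early and used similar re-initiation criteria. From that study's results the section draws two figures. The first puts the expected median at ATI week 15. The second is that "the 75th percentile for time to meeting ART re-initiation criteria will be around week 12-18". It then says what follows: "If the spread in the distribution time to meeting ART re-initiation criteria is less than expected", the PSRT, in consultation with the NIAID DSMB, will consider modifying the study, with altered eligibility criteria as the example, so as to enrich for potential controllers.

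Protocol 4.1.1 models the same endpoint for the power calculation. It uses the placebo arm of a therapeutic vaccine study in early-treated patients (reference 21) and a Weibull survival function exp[-(λt)^p], with λ = exp(-2.932) and p = 2.014. From this, "we estimated the median time to meet re-initiation criteria as 15.6 weeks in the AMP placebo recipients". SAP Section 8 repeats the same parameters and median. Neither document prints a 75th percentile for the Weibull, and neither relates the 11.1.1 figures to it. Section 11.1.1 gives no reference number and no arm for the study it names.

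**The concern.** The two figures in 11.1.1 cannot both hold over the whole stated range. At least half of the distribution lies at or below the median and three quarters at or below the 75th percentile, so the second can never be smaller than the first. With a median at week 15, the lower half of the 12-18 range is excluded.

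The figures stand in the sentence that tells the PSRT what to expect, and the next sentence acts on a spread smaller than expected. A reader who takes 18 weeks as the upper end of the 75th percentile expects a tight distribution. A reader who works from the 4.1.1 model expects a much wider one. The same first 20 participants could look ordinary to one and narrow to the other. What is at stake is an advisory judgement that might lead to a change in who is enrolled. No test, estimate or sample size depends on it.

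**Working it through.** **Inputs.** Median at week 15 and 75th percentile at about week 12-18 (Protocol 11.1.1). λ = exp(-2.932) = 0.05329, p = 2.014 and stated median 15.6 weeks (Protocol 4.1.1; SAP Section 8).

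**Step 1: internal check of 11.1.1.** The 75th percentile must be at least the median, so at least 15. Of the range 12 to 18, only 15 to 18 is possible. This needs no model and no outside source.

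**Step 2: reproduce the plan's own figure.** The Weibull quantile is t(u) = [-ln(1-u)]^(1/p) / λ. For the median, (ln 2)^(1/2.014) / 0.05329 = 0.8336 / 0.05329 = 15.64 weeks. The plan's 15.6 is reproduced.

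**Step 3: the other quartiles of the planning model.**
- 25th percentile: [ln(4/3)]^(1/2.014) / 0.05329 = 0.5387 / 0.05329 = 10.1 weeks.
- 75th percentile: (ln 4)^(1/2.014) / 0.05329 = 1.1761 / 0.05329 = 22.1 weeks.
- Interquartile width: 22.07 - 10.11 = 12.0 weeks.

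These are for the placebo model, that is, with no VRC01 effect.

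**Step 4: compare with the literal reading of 11.1.1.**

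| Quantity | 11.1.1 read literally | Planning Weibull |
|---|---|---|
| Median | 15 | 15.6 |
| 75th percentile | at most about 18 | 22.1 |
| Median to 75th percentile | at most about 3 weeks | 6.4 weeks |
| Not yet meeting criteria at week 18 | at most 25% | 39.9% |

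The last entry is exp[-(0.05329 × 18)^2.014] = exp(-0.9196) = 0.399. The small difference in medians does not explain the gap: rescaling the model to a median of exactly 15 with the same shape gives a 75th percentile of 21.2 weeks. A Weibull with median 15 and 75th percentile 18 needs shape ln(ln 4 / ln 2) / ln(18/15) = 0.693 / 0.182 = 3.8, not 2.014.

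**Step 5: the alternative reading.** Suppose 12-18 was meant as the interquartile range. The label is then wrong, and the width is 6 weeks against 12.0 for the model. That difference is not by itself a contradiction, because a fitted curve and a sample interquartile range can differ when a few times are long. An invented set of 15 times shows this: 6, 9, 11, 12, 12, 13, 14, 15, 15, 16, 17, 18, 19, 24, and one censored at 40. Its sample quartiles, with the censored time counted as the longest, are 12, 15 and 17.5. Its maximum-likelihood Weibull has shape 2.05 and quartiles 10.1, 15.5 and 21.7, close to the planning model. The set is illustrative only and is not the source study's data.

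**The case against.** The strongest reply is that this is a labelling slip. The figures 15 and 12-18 are symmetric, as in a median with its interquartile range, and the text says around. On that reading nothing is impossible, and Step 5 shows that nothing need conflict with 4.1.1 either. This is plausible, and the documents do not exclude it. It does not save the sentence, which calls the range a 75th percentile. Nor does around help, since loosening the ends of a range does not allow a 75th percentile three weeks below the median.

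A second reply is that the comparator in 11.1.1 is the distribution observed in the source study, so reviewers with those data need not rely on the printed figures, and 4.1.1 offers another full distribution. That stands, and it limits the consequence. So do these facts: the PSRT only considers changes, no cut-off is set, the DSMB is consulted, and with planned enrolment of 16-61 the first 20 may not be reached.

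A reader might go further and infer that 11.1.1 contradicts the planning model, so that either the Weibull or the stated power is wrong. The documents do not support that. Section 11.1.1 states an expectation for participants as a whole from an uncited study. Section 4.1.1 fits one placebo arm and applies the result to AMP placebo recipients. The descriptions are similar, but nothing says that study and arm are the same, and the power calculation does not use the 11.1.1 figures. A reader might also infer that the review would prompt changes too often or too seldom. With no decision rule written down, that cannot be calculated from the documents.

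**Conclusion.** The sentence in Protocol 11.1.1 is wrong as written: with a median at week 15, a 75th percentile from week 12 to just under 15 is impossible. That part is certain and rests on one sentence alone.

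The difference from the planning model is conditional. If 11.1.1 means a 75th percentile of at most about 18 weeks, it is about 4 weeks earlier than the model's 22.1. This comparison assumes no VRC01 effect and assumes that the two passages describe comparable populations, which the documents do not establish. If 12-18 is a mislabelled interquartile range, there need be no conflict, but the label must change. Only the source data can settle which was meant.

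The correction should be made because this is the stated expectation for a named review that may lead to altered eligibility. It gives no reason to change the Weibull model, the power tables, the sample size or any planned analysis.

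**What to change.** Check the source study's data and rewrite the sentence in 11.1.1 to give its observed 25th, 50th and 75th percentiles, each correctly labelled, with the study and arm cited. Add a sentence on how these relate to the 4.1.1 planning model, whose quartiles are about 10, 15.6 and 22 weeks with no VRC01 effect: whether the study and arm are the same and, if so, why the observed and fitted quartiles differ. The cost is one look at existing data and one or two sentences of text. It needs no new data collection, no additional review and no recalculation of power.

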3.2 Objectives and endpoints

3.2.1 Primary objectives and endpoints

Primary objective 1

- To evaluate the effect of early ART initiation, with or without having received VRC01 in the immediate pre-HIV acquisition period and/or during early

infection on the time to meeting ART re-initiation criteria in participants undergoing ATI

Primary endpoint 1

- Time to meeting criteria for ART re-initiation
- Frequency of sustained post-treatment HIV control, defined as ≥ 24 weeks off ART without meeting ART re-initiation criteria

Primary objective 2

- To evaluate the safety of ATI among HVTN 805/HPTN 093 participants

Primary endpoint 2

- Laboratory measures of safety, adverse events (AEs), SAEs, and rates of discontinuation

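### The PSRT's first-20 review judges controllers by the spread of restart times, with no statistic, margin or consistent benchmark; a week-24 count would serve its aim better

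*Protocol*

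**What the plan says.** Protocol 11.1.1 directs the PSRT to "review the distribution of time to meeting ART re-initiation criteria in the first 20 HVTN 805/HPTN 093 participants". The yardstick is an outside study of people treated early, since the team must "assess whether the distribution is comparable to that observed in an NIH intramural therapeutic HIV vaccine study". For the centre of the distribution, the section's stated expectation is "the median time to meeting ART re-initiation criteria in HVTN 805/HPTN 093 will be at ATI week 15". For the upper quartile it offers only a range, namely "the 75th percentile for time to meeting ART re-initiation criteria will be around week 12-18". The condition for going further reads "If the spread in the distribution time to meeting ART re-initiation criteria is less than expected". In that case the PSRT, consulting the DSMB, considers ways to modify the study, with altered eligibility as an example, "with the aim to further enrich for potential controllers".

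Two other places bear on this. Protocol 4.1.1 fits a Weibull to the placebo arm of a therapeutic vaccine study, from which "we estimated the median time to meet re-initiation criteria as 15.6 weeks in the AMP placebo recipients". Protocol 3.2.1 makes sustained post-treatment control part of the first primary endpoint, "defined as ≥ 24 weeks off ART without meeting ART re-initiation criteria".

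Neither document says which measure of spread is meant, how large a shortfall matters, or how participants still off ART enter the calculation. Neither gives the review's operating characteristics. The SAP does not mention this review.

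**The concern.** The aim is to learn whether there are too few controllers, but the condition is written in terms of spread. Spread also depends on how fast and how uniformly the other participants rebound, and an interquartile range takes in the upper tail only through the 75th percentile. Without a margin, a sample of 20 drawn from exactly the expected distribution falls short of the expected spread roughly as often as not.

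At stake is a possible change of eligibility in a study planned for 16 to 61 people, prompted by sampling noise, or a real shortage of controllers that the chosen measure shows poorly.

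**Working it through.** **Inputs.** Weibull λ = exp(−2.932) = 0.0533 and p = 2.014 (Protocol 4.1.1); n = 20, median 15 and 75th percentile 12-18 (11.1.1); control at 24 weeks (3.2.1); scenario sizes (Table 4-1).

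**1. The plan's own figures.** The quantile is t(u) = (−ln(1−u))^(1/p)/λ. The median is 15.64 weeks (stated 15.6). Simulated log-rank power for a 60% hazard reduction at 50% enrolment is 72.3% and 63.0% (stated 72% and 62%). The model reproduces.

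**2. What the model implies.** Quartiles are 10.1 and 22.1 weeks, so the IQR is 12.0 weeks; the SD is 8.6 weeks. S(24) = exp(−(0.0533 × 24)^2.014) = 19.4%, or 20 × 0.194 = 3.9 controllers expected among 20.

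**3. The literal condition when the data match that model** (200,000 simulated samples of 20, no censoring):

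| Spread measure | P(sample spread < model value) |
|---|---|
| IQR, linear interpolation (R default) | 64% |
| IQR, averaged ECDF (SAS default) | 55% |
| IQR, median-unbiased | 52% |
| IQR, (n+1)p rule | 46% |
| SD | 55% |

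If weeks 12-18 is read as an expected spread of 6 weeks, P(IQR < 6) is about 1-2%.

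**4. Spread as a marker of controllers.** In the same samples, IQR and the number of controllers correlate at 0.60. Fix exactly 4 controllers of 20, set at 72 weeks, and draw the rest from the Weibull below week 24: the IQR (linear) still falls short of 12.0 in 70% of samples, although the number of controllers is as planned.

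**5. A count at week 24.** Let X be the number of 20 still off ART without having met criteria, X ~ Binomial(20, s). Then P(X ≤ 1) = (1−s)^20 + 20s(1−s)^19.

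| True s | P(X ≤ 1) |
|---|---|
| 19.4% (4.1.1 Weibull) | 7.8% |
| 5% | 74% |
| 2% | 94% |

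**6. Like for like.** Set each rule's cut-off so that it is met 7.8% of the time under the 4.1.1 Weibull. Then keep the shape and shorten the times until 5% exceed week 24. The IQR rule is met in 34-36% of samples (by quantile definition), the SD rule in 59%, and the count rule in about 73-74%.

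**7. The benchmark.** A 75th percentile cannot lie below the median, so the part of 12-18 under week 15 cannot hold. At the upper end, a Weibull with median 15 and 75th percentile 18 has p = ln(ln 4/ln 2)/ln(18/15) = 3.80 and S(24) = exp(−ln 2 × (24/15)^3.80) = 1.6%. That is 0.3 controllers of 20 against 3.9 under 4.1.1, and the 0-or-1 rule would then be met 96% of the time.

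**8. Reach and dropout.** Table 4-1 totals are 7+14 = 21, 13+27 = 40, 20+41 = 61, 9+7 = 16, 18+14 = 32 and 26+21 = 47; five of the six reach 20. With 20% per year censoring (4.1.1), at most 1 − 0.8^(24/52) = 9.8% would be censored by week 24, about 2 of 20. That matters for a cut-off of 1.

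**The case against.** The strongest reply is that there is no mechanical rule. The PSRT judges whether the whole distribution is comparable and then considers options with the DSMB. It sees restart-time summaries twice a month, and the SAP's DSMB reports include the cumulative incidence of meeting criteria, from which the week-24 fraction can be read. This stands: the 46-64% describes a literal reading, not how often the study would be changed. It also depends on the benchmark (1-2% for a 6-week spread) and on pooling the arms: if two thirds of the first 20 are VRC01 recipients with hazard ratios of 0.4 to 0.6, the figure is 16-36% (IQR, linear). What judgement cannot supply is the missing definition of expected spread.

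A reader might infer more than the documents support:

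- That this is the only data-driven route to modifying the study. The next paragraph of 11.1.1 sends failures to re-suppress and related Grade 4 events for review of possible modification.
- That the review is barely reachable. Five of six scenarios reach 20, and four leave at least 12 further participants.
- That spread is unrelated to controllers. The correlation of 0.60 says otherwise.
- That near-universal control would prompt enrichment. An IQR can then be very small, but a committee looking at the whole distribution would see the late median.

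A further fair objection is that the count rule has the same benchmark problem: 8% under 4.1.1 and 96% under the other reading. That also stands, and it is why reconciliation has to come first.

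**Conclusion.** The point holds as an inexpensive improvement to an advisory review; it does not show that the study would be altered by chance. Spread is an indirect marker with no stated measure or margin. Against the 4.1.1 model the literal condition is met in about 46-64% of on-plan samples, and against a 6-week spread in about 1-2%. At an equal 7.8% rate under the planning model, the week-24 count picks up a fall to 5% controllers about twice as often as the IQR and clearly more often than the SD.

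The result assumes that the vaccine study behind 4.1.1 is the one named in 11.1.1, or comparable to it (11.1.1 gives no citation); that restart times are Weibull; and that censoring before week 24 is ignored. The 5% comparison also assumes an unchanged Weibull shape.

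**What to change.** In 11.1.1, in this order:

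1. Reconcile the stated expectation (median 15, 75th percentile 12-18) with the 4.1.1 model (75th percentile 22.1 weeks, 19.4% beyond week 24), and cite the source study.
2. Replace spread with a count, for example: *Once each of the first 20 participants has reached ATI week 24 or met re-initiation criteria, the PSRT will count those still off ART without having met criteria at week 24. A count of 0 or 1 will be taken as guidance that the PSRT, in consultation with the DSMB, should consider ways to enrich for potential controllers.* The cut-off is to be confirmed after step 1.
3. State how often the rule is met under the reconciled benchmark, next to 74% and 94% for true proportions of 5% and 2%.
4. Say how participants censored before week 24 are counted.
5. Say that the review does not take place if fewer than 20 enrol, as in one of the six planning scenarios.

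No extra visits or data are needed. The costs are a cut-off agreed in advance and a later review, which in a small recruitment pool leaves less enrolment to influence.
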